**Table 5: Dose Modification and Toxicity Management Guidelines for Immune-related AEs Associated with Pembrolizumab**

General instructions:				

 
1. Corticosteroid taper should be initiated upon AE improving to Grade 1 or less and continue to taper over at least 4 weeks.
 
2. For situations where pembrolizumab has been withheld, pembrolizumab can be resumed after AE has been reduced to Grade 1 or 0 and corticosteroid has been tapered. Pembrolizumab should be permanently discontinued if AE does not resolve within 12 weeks of last dose or corticosteroids cannot be reduced to <math>\leq 10</math> mg prednisone or equivalent per day within 12 weeks.
 
3. For severe and life-threatening irAEs, IV corticosteroid should be initiated first followed by oral steroid. Other immunosuppressive treatment should be initiated if irAEs cannot be controlled by corticosteroids.
 
				
Immune-related AEs	Toxicity grade or conditions (CTCAEv4.0)	Action taken to pembrolizumab	irAE management with corticosteroid and/or other therapies	Monitor and follow-up
Pneumonitis	Grade 2	Withhold	
 
• Administer corticosteroids (initial dose of 1-2 mg/kg prednisone or equivalent) followed by taper
 
	
 
• Monitor participants for signs and symptoms of pneumonitis
 
• Evaluate participants with suspected pneumonitis with radiographic imaging and initiate corticosteroid treatment
 
• Add prophylactic antibiotics for opportunistic infections
 

	Grade 3 or 4, or recurrent Grade 2	Permanently discontinue		
Diarrhea / Colitis	Grade 2 or 3	Withhold	
 
• Administer corticosteroids (initial dose of 1-2 mg/kg prednisone or equivalent) followed by taper
 
	
 
• Monitor participants for signs and symptoms of enterocolitis (ie, diarrhea, abdominal pain, blood or mucus in stool with or without
 

	Grade 4	Permanently discontinue		
fever) and of bowel perforation (ie, peritoneal signs and ileus).
 
 
• Participants with <math>\geq</math> Grade 2 diarrhea suspecting colitis should consider GI consultation and performing endoscopy to rule out colitis.
 
• Participants with diarrhea/colitis should be advised to drink liberal quantities of clear fluids. If sufficient oral fluid intake is not feasible, fluid and electrolytes should be substituted via IV infusion.
 

AST / ALT elevation or Increased bilirubin	Grade 2	Withhold	
 
• Administer corticosteroids (initial dose of 0.5- 1 mg/kg prednisone or equivalent) followed by taper
 
	
 
• Monitor with liver function tests (consider weekly or more frequently until liver enzyme value returned to baseline or is stable
 

	Grade 3 or 4	Permanently discontinue	
 
• Administer corticosteroids (initial dose of 1-2 mg/kg prednisone or equivalent) followed by taper
 
	
Type 1 diabetes mellitus (T1DM) or Hyperglycemia	Newly onset T1DM or Grade 3 or 4 hyperglycemia associated with evidence of $\beta$ -cell failure	Withhold	
 
• Initiate insulin replacement therapy for participants with T1DM
 
• Administer anti-hyperglycemic in participants with hyperglycemia
 
	
 
• Monitor participants for hyperglycemia or other signs and symptoms of diabetes.
 

Hypophysitis	Grade 2	Withhold	
 
• Administer corticosteroids and initiate hormonal replacements as clinically indicated.
 
	
 
• Monitor for signs and symptoms of hypophysitis (including hypopituitarism and adrenal insufficiency)
 

	Grade 3 or 4	Withhold or permanently discontinue 		
Hyperthyroidism	Grade 2	Continue	
 
• Treat with non-selective beta-
 
	
 
• Monitor for signs and symptoms of thyroid
 

	Grade 3 or 4	Withhold or permanently discontinue 	blockers (eg, propranolol) or thionamides as appropriate	disorders.
Hypothyroidism	Grade 2-4	Continue	
 
Initiate thyroid replacement hormones (eg, levothyroxine or liothyronine) per standard of care
 
	
 
Monitor for signs and symptoms of thyroid disorders.
 

Nephritis and Renal dysfunction	Grade 2	Withhold	
 
Administer corticosteroids (prednisone 1-2 mg/kg or equivalent) followed by taper.
 
	
 
Monitor changes of renal function
 

	Grade 3 or 4	Permanently discontinue		
Myocarditis	Grade 1 or 2	Withhold	
 
Based on severity of AE administer corticosteroids
 
	
 
Ensure adequate evaluation to confirm etiology and/or exclude other causes
 

	Grade 3 or 4	Permanently discontinue		
All other immune-related AEs	Intolerable/persistent Grade 2	Withhold	
 
Based on type and severity of AE administer corticosteroids
 
	
 
Ensure adequate evaluation to confirm etiology and/or exclude other causes
 

	Grade 3	Withhold or discontinue based on the type of event. Events that require discontinuation include and not limited to: Gullain-Barre Syndrome, encephalitis		
	Grade 4 or recurrent Grade 3	Permanently discontinue		

1. Withhold or permanently discontinue pembrolizumab is at the discretion of the investigator or treating physician.
 
NOTE: For participants with Grade 3 or 4 immune-related endocrinopathy where withhold of pembrolizumab is required, pembrolizumab may be resumed when AE resolves to ≤ Grade 2 and is controlled with hormonal replacement therapy or achieved metabolic control (in case of T1DM).
				

### 5.3. Timing of Dose Administration

Pembrolizumab should be administered on Day 1 of each cycle after all procedures/assessments have been completed.

Pembrolizumab 200 mg will be administered as a 30 minute IV infusion every 3 weeks. Every effort should be made to target infusion timing to be as close to 30 minutes as possible. However, given the variability of infusion pumps, a window of -5 minutes and +10 minutes is permitted (i.e., infusion time is 30 minutes: -5 min/+10 min).

The Pharmacy Manual contains specific instructions for the preparation of the pembrolizumab infusion fluid and administration of infusion solution.

Decitabine will be administered at a dose of 20 mg/m^2 by intravenous infusion over approximately 1 hour repeated daily ordinarily on days 8 through 12 and 15 through 19 of alternative cycles (ie: cycles 1, 3, 5, 7). Decitabine may be given +/- 3 days, if needed for administrative or logistical issues. Decitabine should be repeated every 6 weeks. Patients may be premedicated with standard anti-emetic therapy. Every effort should be made to target infusion timing to be as close to 60 minutes as possible. However, given the variability of infusion pumps, a window of -5 minutes and +10 minutes is permitted (i.e., infusion time is 60 minutes: -5 min/+10 min).

These timings may change in accordance with section 5.2 above.

#### **5.4. Randomization or Treatment Allocation**

All patients will receive the same treatment.

This is an open-label trial; therefore, the sponsor, investigator, care team and subject will all know the treatment administered.

#### **5.5. Concomitant Medications/Vaccinations (allowed & prohibited)**

Medications or vaccinations specifically prohibited in the exclusion criteria are not allowed during the ongoing trial. If there is a clinical indication for one of these or other medications or vaccinations specifically prohibited during the trial, discontinuation from trial therapy or vaccination may be required. The investigator should discuss any questions regarding this with the Merck Clinical team. The final decision on any supportive therapy or vaccination rests with the investigator and/or the subject's primary physician.

#### **Acceptable Concomitant Medications**

All treatments that the investigator considers necessary for a subject's welfare may be administered at the discretion of the investigator in keeping with the community standards of medical care. All concomitant medication will be recorded in the electronic medical record including all prescription, over-the-counter (OTC), herbal supplements, and IV medications and fluids. If changes occur during the trial period, documentation of drug dosage, frequency, route, and date will also be included in the electronic medical record.

All concomitant medications received within 28 days before the first dose of trial treatment and 30 days after the last dose of trial treatment should be recorded.

#### **Prohibited Concomitant Medications**

Subjects are prohibited from receiving the following therapies during the Screening and Treatment Phase of this trial:

- Antineoplastic systemic chemotherapy or biological therapy
- Immunotherapy not specified in this protocol
- Chemotherapy not specified in this protocol
- Investigational agents other than pembrolizumab or decitabine
- Radiation therapy

Note: Radiation therapy to a symptomatic solitary lesion or to the brain may be allowed at the investigator's discretion.

- Live vaccines within 30 days prior to the first dose of trial treatment and while participating in the trial. Examples of live vaccines include, but are not limited to, the following: measles, mumps, rubella, varicella/zoster, yellow fever, rabies, BCG, and typhoid vaccine.
- Systemic glucocorticoids for any purpose other than to modulate symptoms from an event of clinical interest of suspected immunologic etiology. The use of physiologic doses of corticosteroids may be approved after consultation with the investigator.

Subjects who, in the assessment by the investigator, require the use of any of the aforementioned treatments for clinical management should be removed from the trial. Subjects may receive other medications that the investigator deems to be medically necessary.

There are no prohibited therapies during the Post-Treatment Active Surveillance follow-up stage.

## **5.6. Rescue Medications & Supportive Care**

### **Supportive Care Guidelines**

Subjects should receive appropriate supportive care measures as deemed necessary by the treating investigator. This includes standard prophylaxis for infection and tumor lysis. Suggested supportive care measures for the management of adverse events with potential immunologic etiology are outlined below. Where appropriate, these guidelines include the use of oral or intravenous treatment with corticosteroids as well as additional anti-inflammatory agents if symptoms do not improve with administration of corticosteroids. Note that several courses of steroid tapering may be necessary as symptoms may worsen when the steroid dose is decreased. For each disorder, attempts should be made to rule out other causes such as metastatic disease or bacterial or viral

infection, which might require additional supportive care. The treatment guidelines are intended to be applied when the investigator determines the events to be related to pembrolizumab.

Note: if after the evaluation the event is determined not to be related, the investigator does not need to follow the treatment guidance (as outlined below). Refer to Section 5.2 for dose modification.

It may be necessary to perform conditional procedures such as bronchoscopy, endoscopy, or skin photography as part of evaluation of the event.

**Pneumonitis:**

For **Grade 2 events**, treat with systemic corticosteroids. When symptoms improve to Grade 1 or less, steroid taper should be started and continued over no less than 4 weeks.

For **Grade 3-4 events**, immediately treat with intravenous steroids. Administer additional anti-inflammatory measures, as needed.

Add prophylactic antibiotics for opportunistic infections in the case of prolonged steroid administration.

**Diarrhea/Colitis:**

Subjects should be carefully monitored for signs and symptoms of enterocolitis (such as diarrhea, abdominal pain, blood or mucus in stool, with or without fever) and of bowel perforation (such as peritoneal signs and ileus).

All subjects who experience diarrhea/colitis should be advised to drink liberal quantities of clear fluids. If sufficient oral fluid intake is not feasible, fluid and electrolytes should be substituted via IV infusion. For Grade 2 or higher diarrhea, consider GI consultation and endoscopy to confirm or rule out colitis.

For **Grade 2 diarrhea/colitis**, administer oral corticosteroids.

For **Grade 3 or 4 diarrhea/colitis**, treat with intravenous steroids followed by high dose oral steroids.

When symptoms improve to Grade 1 or less, steroid taper should be started and continued over no less than 4 weeks.

**Type 1 diabetes mellitus (if new onset, including diabetic ketoacidosis [DKA]) or  $\geq$  Grade 3 Hyperglycemia, if associated with ketosis (ketonuria) or metabolic acidosis (DKA)**

For **T1DM or Grade 3-4 Hyperglycemia**

Insulin replacement therapy is recommended for Type I diabetes mellitus and for Grade 3-4 hyperglycemia associated with metabolic acidosis or ketonuria.

Evaluate patients with serum glucose and a metabolic panel, urine ketones, glycosylated hemoglobin, and C-peptide.

### **Hypophysitis:**

For **Grade 2** events, treat with corticosteroids. When symptoms improve to Grade 1 or less, steroid taper should be started and continued over no less than 4 weeks. Replacement of appropriate hormones may be required as the steroid dose is tapered.

For **Grade 3-4** events, treat with an initial dose of IV corticosteroids followed by oral corticosteroids. When symptoms improve to Grade 1 or less, steroid taper should be started and continued over no less than 4 weeks. Replacement of appropriate hormones may be required as the steroid dose is tapered.

### **Hyperthyroidism or Hypothyroidism:**

Thyroid disorders can occur at any time during treatment. Monitor patients for changes in thyroid function (at the start of treatment, periodically during treatment, and as indicated based on clinical evaluation) and for clinical signs and symptoms of thyroid disorders.

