## 6.2. On therapy evaluations during induction phase

**Cycles 1-8: before starting each cycle (+/- 3 day window):**

The following assessments will be performed prior to each cycle of pembrolizumab.

- Interval History
- ECOG performance status evaluation
- Structured adverse event assessment
- Concomitant medication review
- Physical exam
- Complete blood count with differential
- Acute care & mineral panels (includes Na, K, Cl, CO2, creatinine, glucose, BUN, phosphorus, magnesium, albumin, and calcium)
- Total protein, CK, Uric Acid, and LDH
- Hepatic panel (includes alkaline phosphatase, ALT, AST, total bilirubin, and direct bilirubin)
- Reticulocyte count

- PT, PTT, fibrinogen
- Pregnancy test for females of childbearing potential

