### 6.4. On therapy evaluations during optional continuation phase

Patients treated on the continuation phase will ordinarily be evaluated, including Structured adverse event assessment, as described in section 6.2, every 4 cycles (*ie:* every 12-13 weeks).

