## 6.5. Post-Induction Treatment Follow-Up

### 6.5.1. Safety Follow-Up Visit (SFV)

The mandatory Safety Follow-Up Visit should be conducted after the eighth cycle of treatment (ie: end of induction phase), or (for patients discontinuing therapy prior to this point) approximately 30 days after the last dose of trial treatment or before the initiation of a new anti-cancer treatment, whichever comes first. All AEs that occur prior to this Safety Follow-Up Visit should be recorded. Subjects with a persistent treatment related AE will be followed until the resolution of the AE or until the beginning of a new anti-neoplastic therapy, whichever occurs first. No new adverse event information will be collected after this safety follow-up visit.

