### 9.1.1. Timing

The AE reporting period for this study begins when the patient takes the first dose of study drug and ends with the safety follow-up visit. If an SAE is present at the safety follow-up visit or within 30 days of the last dose of study drug (whichever is later), it should be followed to resolution or until the Investigator assesses the subject as stable, a new anticancer therapy is initiated, or the subject is lost to follow-up or withdraws consent. Resolution/stable means the subject has returned to baseline state of health or the Investigator does not expect any further improvement or worsening of the event.

All adverse events will be recorded at each examination on the Adverse Event case report forms/worksheets from the time the consent form is signed through the safety follow-up visit.

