## 9.2. Documentation

Investigators will assess the occurrence of AEs and SAEs at all patient evaluation time points during the study. There are ten scheduled patient evaluation time-points; at baseline, after cycles 1-8 and at the safety follow-up visit (see also Appendix G). In addition, all AEs and SAEs whether volunteered by the patient, discovered by study personnel during questioning, or detected through physical examination, clinically significant laboratory test, or other means will be recorded in the patient's medical record.

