## APPENDIX G: Scheduled Clinical Assessments

Trial Period:	Screening Phase	Induction Phase Treatment (Assessment at end of cycle...)								Post-Induction	
		1	2	3	4	5	6	7	8	SFV / Off-study Visits	Contin. Phase (q3mo)
Pre-screening and Consents	X										
Inclusion/Exclusion Criteria	X										
Demographics and Full Medical History	X										
Interval Medical History		X	X	X	X	X	X	X	X	X	X
Focused Physical Exam		X	X	X	X	X	X	X	X	X	X
ECOG Performance Status	Baseline	X	X	X	X	X	X	X	X	X	X
Structured Review of Adverse Events	Baseline	X	X	X	X	X	X	X	X	X	X
Prior and Concomitant Medication Review	X	X	X	X	X	X	X	X	X	X	X
Trial Treatment Administration Log		X	X	X	X	X	X	X	X		
Therapy Response Assessment	X		X		X		X		X	X	X
Bone Marrow Examination* (flow cytometry, morphology)	X		X		X		X		X		
Cytogenetics (bone marrow)	X		If+ @BL		If+ @BL		If+ @BL		X		
Pregnancy Test -- Urine or Serum $\beta$ -HCG	W/in 72 hours of first dose.	X	X	X	X	X	X	X	X	X	X
Acute Care, Mineral and Hepatic Panels	W/in 14 days of first dose	X	X	X	X	X	X	X	X	X	X
Total protein, CK, Uric Acid, LDH, PT, PTT, Fibrinogen, CBC w/ diff, Reticulocyte, Type&Screen.	X	X	X	X	X	X	X	X	X	X	X
CMV IgG, IgM and PCR, HIV serology, Hepatitis serologies,	X										
Thyroid Function (T3, FT4 and TSH), EKG, HLA typing, Urinalysis	X										
Peripheral Blood Flow Cytometry (T/B/NK and AML)	X		X		X		X		X		

"If + @ BL" = Cytogenetics will be checked after cycles 2, 4 and 6 only if abnormal at baseline.

\* = an additional bone marrow examination assessment will be performed on cycle 1 day 8 (+/- 3 days).

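### Section 5.6 asks for periodic thyroid monitoring on treatment, but the visit schedule has no thyroid test after screening, so mild thyroid events in induction may be missed or mistimed

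*Combined protocol and SAP*

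**What the plan says.** Section 5.6, under the thyroid heading, notes that thyroid disorders can arise at any time on treatment. It asks for thyroid function to be monitored at the start, "periodically during treatment, and as indicated based on clinical evaluation". Periodic monitoring and monitoring on clinical indication are separate items, and no interval is given.

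The operational sections read as follows:

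- **6.1** lists thyroid function tests at screening.
- **6.2** introduces the induction list with "The following assessments will be performed prior to each cycle of pembrolizumab". It names blood counts, chemistry, hepatic panel, reticulocytes, coagulation and a pregnancy test, but no thyroid test.
- **6.4** has continuation patients evaluated "as described in section 6.2, every 4 cycles", so it adds none.
- **6.5.1** (safety follow-up visit) names none and closes the window: "No new adverse event information will be collected after this safety follow-up visit".
- **Appendix G** has a row "Thyroid Function (T3, FT4 and TSH), EKG, HLA typing, Urinalysis", marked in the screening column only.

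On recording, 9.1.1 says that the adverse event reporting period "begins when the patient takes the first dose of study drug and ends with the safety follow-up visit". Section 9.2 says: "There are ten scheduled patient evaluation time-points; at baseline, after cycles 1-8 and at the safety follow-up visit". It also provides that events "detected through physical examination, clinically significant laboratory test, or other means will be recorded". Table 7 defines the feasibility outcome as a descriptive summary of the number, severity and duration of all adverse events.

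**The concern.** A site that follows 6.2 and Appendix G to the letter would run no thyroid test after screening, although 5.6 expects repeated ones. Testing on symptoms does not meet that expectation, because 5.6 lists it separately.

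This bears on the primary outcome. All three parts of the Table 7 summary depend on an event being detected, and duration also depends on when it is detected. Among the pembrolizumab events that 11.2.1 counts out of 1562 subjects, hypothyroidism is the most frequent (113, against 45 for pneumonitis). Hepatic events (8 of 1562) have a scheduled laboratory panel before every cycle. A mild thyroid event not found by the safety follow-up visit does not enter the summary. One found late has the wrong onset and duration. With ten patients, one missed event moves a crude frequency by 1/10, or 10 percentage points.

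**Working it through.** **Coverage of the schedule**

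- Evaluation time-points in 9.2: baseline (1) + after cycles 1-8 (8) + safety follow-up visit (1) = 10.
- With a scheduled thyroid test (6.1, 6.2, 6.5.1, Appendix G): 1, at baseline. Without: 10 - 1 = 9.
- Induction length (5.1): 8 cycles x 21 days = 168 days with no scheduled test.
- Continuation, cycles 9-35 (5.9): (35 - 8) x 21 = 567 days by cycle count. The two-year off-study limit in 5.8.2 trims this slightly. New adverse event collection has already ended by then, so this part concerns patient monitoring and not the primary counts.

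A table-extraction fault in Appendix G would not explain the gap. The prose list in 6.2 omits the test independently, and neighbouring Appendix G rows keep their per-cycle marks.

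**What the existing checks cover**

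- Section 9.6 requires a check for events of clinical interest before each dose, using laboratory results and symptoms. Appendix C names hyperthyroidism, hypothyroidism, thyroiditis and thyroid disorder. The scheduled pre-cycle labs contain no thyroid result to review.
- The Appendix C threshold for these events is Grade 3 or above, or Grade 2 or above with dose modification or systemic steroids. The remaining gap is therefore mainly Grade 1-2 events.
- For thyroid events, Table 5 asks for monitoring of signs and symptoms and gives no laboratory schedule.
- The stopping rule in 8.3 counts grade 4 or 5 treatment-related events, so mild thyroid events do not enter it.

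**How often thyroid events might occur**

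Inputs are the counts in 11.2.1 (N = 1562) and the sample size of 10 in 8.2. The plan's own percentages reproduce: 113/1562 = 7.2% and 34/1562 = 2.2%; drug-related, 104/1562 = 6.7% and 30/1562 = 1.9%.

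Expected events = 10p. Chance of at least one = 1 - (1 - p)^10.

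| Event | p | Expected in 10 | Chance of at least one |
|---|---|---|---|
| Hypothyroidism, any cause | 113/1562 = 0.0723 | 0.72 | 1 - 0.9277^10 = 52.8% |
| Hypo- plus hyperthyroidism, any cause | 147/1562 = 0.0941 | 0.94 | 1 - 0.9059^10 = 62.8% |
| Hypo- plus hyperthyroidism, drug-related | 134/1562 = 0.0858 | 0.86 | 1 - 0.9142^10 = 59.2% |

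The combined rows assume that no patient has both conditions. These are chances that an event occurs, not that it is missed. Under the same assumptions, expected missed events lie between 0 (all found through symptoms or unscheduled tests) and 0.94 (none found).

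**The case against.** The strongest reply is that this is an unstated interval and not a contradiction. Section 5.6 is itself protocol text, 6.2 and Appendix G exclude no additional test, and a site that tests under 5.6 breaches nothing. The supportive-care guidance is framed as suggested measures, and nothing in the documents shows that testing was not done. All of that is true, and it limits the consequence. It does not remove the mismatch: the sections that tell staff what to do at each visit implement none of the periodic monitoring.

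Second, whether an asymptomatic thyroid value counts as an adverse event depends partly on the reporting policy cited in 9.1, which is not in the documents. This stands as a limit on the consequence, although 9.2 does provide for recording events found by a clinically significant laboratory test.

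Third, history, physical examination and structured adverse event review take place every cycle, and 9.6 adds the pre-dose check. Symptomatic disease is therefore sought about every 21 days in induction. This also stands, and it confines the gap to mild or silent events and their dates.

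Fourth, the occurrence figures come from pembrolizumab subjects outside this AML combination, and 11.2.1 gives neither their thyroid-testing schedule nor their exposure time. The figures are background only and do not measure the detection loss. The ceiling of 0.94 would require every case to be missed, including serious ones.

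**Conclusion.** The concern holds and is minor. The mismatch between 5.6 and the schedule is plain from the text: one of ten evaluation time-points has a scheduled thyroid test, and none of the nine after treatment starts does. The likely effect is some under-counting or misdating of Grade 1-2 thyroid events during induction in the descriptive adverse event summary.

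The documents do not allow the loss to be quantified. If the 11.2.1 rates transfer to this population and the two conditions do not overlap, it is at most 0.94 expected events in ten patients and probably well below that. The grade 4-5 stopping rule is essentially unaffected. Treatment decisions would change little, since Table 5 continues pembrolizumab for Grade 2-4 hypothyroidism and Grade 2 hyperthyroidism.

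**What to change.** **For this study.** Section 11.3 places it in data analysis only. Report which on-treatment thyroid tests were done and when. If testing was driven by symptoms, describe the thyroid event counts as minimum estimates. The cost is one table or sentence from existing laboratory records.

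**For the schedule or a successor protocol.** Add TSH and FT4 to 6.2 and Appendix G at a stated interval, for example with the assessments after cycles 2, 4, 6 and 8 and at the safety follow-up visit. Add them to 6.4 for patient safety in continuation. The interval is an example, because 5.6 sets none. The cost is a small assay charge on blood already drawn, with no new visit or procedure, and possibly more incidental low-grade findings. No sample size, stopping boundary or error rate changes.
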